6.3. Statistical Analysis

The data collected in this study will be analyzed by the Biostatistics group at the Perlmutter Cancer Center at NYU.

All data will be listed individually by subject. For quantitative parameters, descriptive statistics will include the mean, standard deviation, minimum, median, and maximum. For qualitative parameters, descriptive statistics will include frequency and percentage.

Unless otherwise indicated, the statistical significance will be declared if the two-sided p-value is ≤ 0.05 .

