6.3.4. Immunology Parameters

The data from each of the assays and assessments described in Appendix 4 will be summarized by week of study, using standard descriptive statistical methods – preferably parametric if the distribution of the continuous assay data (possibly after transformation) is compatible with the assumptions of a normal distribution, and non-parametric otherwise. For each immunological marker studied, one of the following 4 transformations will be used: identity (ie, no transformation), square-root, cube root, or log transformation. Choice of the transformation will be made by computing the Anderson-Darling statistic based on the regression model residues using the pooled data. Then the transformation with the lowest Anderson-Darling statistic will be selected as the most normal-like and used in the mixed model analysis.

Scatterplots of the data for the individual subjects, over time, will be constructed to display the patterns; means (or geometric means or medians) with confidence intervals will also be plotted; contingency tables will be used for the categorical assay responses. For baseline and weeks 7 and 13, regression methods (linear or logistic) that accommodate random effects will be used to evaluate the effect of the treatment regimen on the overall levels and on the trends over time – with subject as the random effect and week as the fixed effects. These analyses will be used to evaluate the quantitative effects of the NIVOLUMAB + ipilimumab regimen on immunologic and pharmacodynamic changes due to treatment. While formally proving that the addition of NIVOLUMAB to ipilimumab will increase the probability of clinical benefit is beyond the scope of this trial, the data obtained will be used to test the hypothesis that the magnitude of the proliferating T-cells (as continuous) will increase with NIVOLUMAB added to ipilimumab compared to the prior cohorts of protocol 15651 at Moffitt Cancer Center with NIVOLUMAB alone. Note that the pre and post treatment assays from any given subject that are used in the analysis are always performed on the same plate, thus eliminating a potential confounding factor due to plate-to-plate assay variation.

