Due to the exploratory nature of this trial, there will be no formal adjustments made to account for the multiple statistical testing performed on the 11 surface and intracellular biomarkers under investigation. However, to guard against having a possibly over-inflated overall type I error rate, result sensitivity will be high if 3 or more phenotypic changes occur with addition of ipilimumab at an individual α level of 0.05 each for further studying these phenotypic changes in NIVOLUMAB + ipilimumab treated cells. In the case of doing 11 independent hypothesis testings with an α level of 0.05 each, the probability of having 3 or more significant results by chance will be only about 0.015, whereas, the probability of having at least 1 or 2 significant results is 0.43 or 0.10, respectively

In addition to analyzing the results of these assays as continuous variables, the T-cell proliferation assay results will be classified as “response” or “non-response” to further explore the relationship of immunologic changes with treatment.

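### The immune-marker mixed model in 6.3.4 names only subject as random, so its trend and week-13 tests hold 0.05 only if patients do not truly differ in their change

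*Combined protocol and SAP*

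**What the plan says.** Section 6.3.4 (Immunology Parameters) sets out the model: "For baseline and weeks 7 and 13, regression methods (linear or logistic) that accommodate random effects will be used". The aim and the random part are given as "to evaluate the effect of the treatment regimen on the overall levels and on the trends over time – with subject as the random effect"; the fixed effect is week. No random slope, residual covariance structure, robust standard error or degrees-of-freedom method is named there or elsewhere.

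Section 6.3 sets the general criterion: "the statistical significance will be declared if the two-sided p-value is ≤ 0.05". Section 6.3.4 then declines to adjust for the "multiple statistical testing performed on the 11 surface and intracellular biomarkers under investigation". As its safeguard it looks for three or more changes "at an individual α level of 0.05 each", and puts the chance of three or more among 11 independent tests at about 0.015 (0.43 for at least one, 0.10 for at least two).

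**The concern.** A random intercept lets patients differ in level but gives all of them the same expected change. Whatever is left within a patient is treated as independent noise of equal size at each visit. If patients truly change by different amounts, the trend and the week-13 change carry extra between-patient variance. The model estimates one within-patient variance by pooling that direction with a less variable one, so the standard error for the trend and the late contrast is too small.

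This holds for a single marker, whatever the number of markers tested or the correlation between them. At stake are the p-values and confidence intervals for the secondary immune-response objective and, if these tests feed it, the 0.015 that 6.3.4 offers in place of a multiplicity adjustment.

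**Working it through.** **Inputs from the documents.** Two-sided 0.05 (6.3); 0.05 per marker and 11 markers (6.3.4); three time points, coded 0, 7 and 13; n = 20 (Synopsis and 4.3, up to 25 enrolled).

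**Input the documents do not give.** The between-patient SD of true change relative to the residual SD. Call it k, the SD of true change by week 13 in residual SDs. It is an assumption, varied from 0 to 5.

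**1. The plan's own figure.** With per-test level a, P(3 or more of 11) = 1 − Σ(j=0 to 2) C(11,j) a^j (1−a)^(11−j). At a = 0.05 this is 1 − (0.5688 + 0.3293 + 0.0867) = 0.0152. The other two figures, 0.431 and 0.102, also reproduce.

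**2. Trend test, linear patient slopes.** The times have mean 6.67 and Sxx = 84.67. Let λ = slope variance × Sxx / residual variance, so λ = k² × 84.67/169 = 0.501k². Each patient contributes two within-patient directions. The linear one has variance proportional to 1 + λ and the other to 1. The random-intercept model pools them to 1 + λ/2. Hence

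true variance / model variance = (1 + λ)/(1 + λ/2), with a ceiling of 2,

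large-sample level = 2[1 − Φ(1.96/√ratio)].

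Example, k = 1: λ = 0.501, ratio = 1.501/1.2505 = 1.20, level 0.074. Example, k = 3: λ = 4.51, ratio = 5.51/3.255 = 1.69, level 0.132.

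Simulated levels with no mean change (n = 20, 40,000 trials per setting):

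| k | Trend and week 13 | 2-df week test |
|---|---|---|
| 0 | 0.05 | 0.05 |
| 0.5 | 0.057 | – |
| 0.75 | 0.065 | – |
| 1 | 0.073 | 0.051 |
| 1.5 | 0.093 | 0.057 |
| 2 | 0.11 | 0.060 |
| 3 | 0.13 | 0.068 |
| 5 | 0.15 | 0.079 |

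The limit for very large k is about 0.17. Runs with n = 17 or 25, or with times 1/7/13, agree within 0.01. REML random-intercept fits gave about 0.09 at λ = 1 and 0.13 at λ = 4.

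**3. Week 7 minus baseline, same slopes.** The true variance is proportional to 2 + (7/13)²k² = 2 + 0.290k², and the model uses 2 + 0.501k². The ratio is below 1, so this test is conservative: simulated 0.019 to 0.041 for k of 1 or more.

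**4. Step-shaped differences (complete by week 7).** For week 13 minus baseline the ratio is (2 + k²)/(2 + 2k²/3), with a ceiling of 1.5. The large-sample level at that ceiling is 2[1 − Φ(1.96/1.225)] = 0.11. Simulated levels for the trend and week-13 tests run from about 0.05 to 0.115.

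**5. Comparator.** A one-sample t test on each patient's own contrast gave 0.047 to 0.053 across these settings.

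**6. Effect on the three-or-more rule**, under the plan's own independence assumption:

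| Per-test level | P(3 or more of 11) |
|---|---|
| 0.05 | 0.015 |
| 0.06 | 0.025 |
| 0.075 | 0.044 |
| 0.10 | 0.090 |

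**7. Cost if the random intercept were exactly right.** For a linear change of d residual SDs by week 13, the noncentrality is d√(20 × 84.67)/13, which is 2.85 at d = 0.9 and 3.17 at d = 1.0. Moving from 38 to 19 degrees of freedom takes power from 0.79 to 0.77 and from 0.87 to 0.85.

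**The case against.** Several objections have force.

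- **Size.** A reader might infer that the true level is 0.09 to 0.15. The documents do not support that as a general result. It needs linear slopes with k of about 1.5 to 5, and no marker variance is reported. Smaller slopes give about 0.057 to 0.073.
- **Which test.** No contrast is named. With week categorical, the single 2-df test per marker is a natural choice and is only mildly affected. The stated interest in trends does, however, support a trend test.
- **The model.** A random slope is not expressly excluded. A single random effect for subject is ordinarily a random intercept, and if more is meant the plan needs to say so.
- **Heterogeneity.** A reader might infer that the plan itself expects different true changes, because "the T-cell proliferation assay results will be classified as “response” or “non-response". That does not follow: cutting a noisy measurement at a 20% increase (6.3.4.1) yields both groups even when every true change is identical.
- **Link to the rule.** The three-or-more rule counts changes seen when ipilimumab is added. That may mean the comparison with the earlier nivolumab cohorts, which was not simulated. So a reader cannot conclude that 0.015 is wrong, only that it is not secured if these within-patient tests feed the rule.
- **Stakes.** 6.3.4 calls the trial exploratory and uses the rule to choose changes for further study. The Synopsis describes immune response as summarised descriptively. No primary endpoint or stopping rule depends on this.

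These points limit the size and importance of the concern. They leave the mechanism standing: the model as ordinarily read does not guarantee 0.05 for a test of trend.

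**Conclusion.** The concern holds in a conditional form. For continuous markers, the trend and week-13 tests from the stated model have level 0.05 only when patients share the same true change. Otherwise the level is above 0.05: about 0.06 to 0.15 for linear slopes with k from 0.5 to 5, and about 0.05 to 0.115 for step-shaped differences. The 2-df week test stays at about 0.05 to 0.08, and the week-7 contrast errs on the safe side under slopes.

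These figures rest on Gaussian data, complete observations, n = 20 and an assumed k. The logistic branch was not assessed. Severity is modest because the analysis is exploratory, but the plan quotes an error rate and the remedy is nearly free.

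**What to change.** In 6.3.4, for the continuous markers, specify week as a categorical fixed effect, an unstructured within-subject covariance across the three time points, and Kenward-Roger degrees of freedom. With complete data this is equivalent to a t test on each per-patient contrast. With missing visits the two differ, so the model should be the stated method.

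Name the single contrast per marker that enters the three-or-more rule, and say whether the rule concerns within-patient change or the comparison with the earlier cohorts. Give the logistic branch its own specification.

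The cost is SAP wording and a small change to the SAS code, with no change to data collection. The statistical price is 19 instead of 38 degrees of freedom, which is the power loss of about 0.02 shown in step 7.

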1.4. Clinical Summary

Prior clinical studies have been conducted with NIVOLUMAB in combination with a peptide vaccine. In this clinical study we will administer NIVOLUMAB in combination with IPILIMUMAB for resected melanoma.

There are currently no open adjuvant trials for children 16-21 years of age with resected high risk melanoma. In prior adjuvant trials conducted by the investigator at Moffitt Cancer Center, such patients ages 16-21 have been routinely included. That population is also treated in the community with adjuvant high dose interferon alpha, which has minimal efficacy in overall survival. In a recently published study, 33 pediatric patients under 21 were treated with ipilimumab immunotherapy (Merchant MS, Wright M, Baird K, Wexler LH, Rodriguez-Galindo C, Bernstein D, Delbrook C, Lodish M, Bishop R, Wolchok JD, Streicher H, Mackall CL. [Phase I Clinical Trial of Ipilimumab in Pediatric Patients with Advanced Solid Tumors](#). Clin Cancer Res. 2016 Mar 15;22(6):1364-70. doi: 10.1158/1078-0432.CCR-15-0491. Epub 2015 Nov 3. PMID: 26534966) demonstrating that the toxicity was quite similar to that seen in adult patients over 21. There is no reason to postulate that the side effects of nivolumab would be any different in the 16-21 population than in an older cohort of resected melanoma patients. The only other alternative for these patients would be off-protocol ipilimumab adjuvant therapy at the FDA approved 10 mg/kg dose, which has a 41% rate of grades 3-4 toxicity, regarded by many as a very toxic regimen¹³. Therefore, given the prior safe experience of the investigator with the age 16-21 population being treated

on immunotherapy adjuvant melanoma trials, the safety of ipilimumab alone documented in the literature in this cohort, the lack of effective or non-toxic alternative therapy available, it is felt that it is appropriate to include the age 16-21 population in the current trial.

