1.4.2. Rationale for the Original NIVOLUMAB + Peptide Vaccine Clinical Study

Clinical data indicated a potential for treatment with NIVOLUMAB in combination with a peptide vaccine to augment the T-cell immune response against specific melanoma antigens and result in antitumor effects that might prolong time to relapse in patients at very high risk of recurrence. The

previous experience did not justify the inclusion of a peptide vaccine in the current cohort of patients with resected melanoma, so the current cohort includes patients treated with NIVOLUMAB + ipilimumab.

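### The cross-trial T-cell hypothesis in section 6.3.4 is labelled as the effect of adding nivolumab, but its comparator can only show the effect of adding ipilimumab, and no nivolumab-alone cohort is described

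*Combined protocol and SAP*

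**What the plan says.** Section 6.3.4 (Immunology Parameters) accepts that formal proof that "the addition of NIVOLUMAB to ipilimumab will increase the probability of clinical benefit is beyond the scope of this trial". The hypothesis set next is that T-cell proliferation, taken as a continuous measure, "will increase with NIVOLUMAB added to ipilimumab compared to the prior cohorts of protocol 15651 at Moffitt Cancer Center with NIVOLUMAB alone".

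The only model in that section is a regression for baseline and weeks 7 and 13, with subject as a random effect and week as a fixed effect. The section adds that the pre- and post-treatment assays "from any given subject that are used in the analysis are always performed on the same plate", to remove plate-to-plate variation.

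The rule for the 11 biomarkers, also in 6.3.4, is worded the other way round: it applies if "3 or more phenotypic changes occur with addition of ipilimumab at an individual α level of 0.05 each".

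Section 6.3 declares significance at a two-sided p-value of 0.05 or less unless otherwise indicated.

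On earlier experience, section 1.4 says: "Prior clinical studies have been conducted with NIVOLUMAB in combination with a peptide vaccine". Section 1.4.2 says the "previous experience did not justify the inclusion of a peptide vaccine in the current cohort of patients". Section 1.4.3 describes cohorts 4 and 5 of the predecessor trial at Moffitt, both treated with nivolumab plus ipilimumab. Section 2.4.2 mentions vaccine plus nivolumab in an adjuvant study, CA209007.

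**The concern.** The hypothesis names one effect and the comparator identifies another. To learn what nivolumab adds to ipilimumab, one needs a group given ipilimumab without nivolumab, and none is planned. Against nivolumab alone, the extra component is ipilimumab.

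The comparator itself cannot be located in the documents. A reader cannot tell which cohorts of 15651 are meant, what they received, how many subjects they hold, or when their samples were taken.

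At stake is the label on an exploratory immune result. Followed as written, the plan would attach a p-value to a non-randomised comparison across trials under the name of an effect that the comparison does not estimate.

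**Working it through.** **Direction of the contrast.** Let N be nivolumab, I ipilimumab, V vaccine, and M(.) the mean T-cell response under a regimen.

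- Effect of adding nivolumab to ipilimumab: M(N+I) − M(I). This needs an ipilimumab-alone group.
- Effect of adding ipilimumab to nivolumab: M(N+I) − M(N). This needs a nivolumab-alone group.

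The comparator named in 6.3.4 is nivolumab alone, so only the second is available. The order is not an isolated slip: 6.3.4 uses it in the clause on clinical benefit and again in the hypothesis, and then reverses it in the 11-marker rule.

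**Identity of the comparator.** What the documents say about earlier nivolumab cohorts in resected patients:

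| Source | Regimen described | Tied to 15651 by name? |
|---|---|---|
| Section 1.4.3, cohort 4 | Nivolumab + ipilimumab, 20 patients | Yes |
| Section 1.4.3, cohort 5 | Nivolumab + ipilimumab for 12 weeks, then nivolumab alone; 20 patients | As cohort 5 at Moffitt, following cohort 4 |
| Section 1.4.2 | Nivolumab + peptide vaccine | No |
| Section 2.4.2, CA209007 | Vaccine + nivolumab | No |

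Nivolumab alone appears only as cohort 5 maintenance, after combination induction. That is not a nivolumab-alone comparator for weeks 7 to 13.

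If vaccine-treated cohorts are what is meant, the contrast becomes

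M(N+I) − M(N+V) = [M(N+I) − M(N)] − [M(N+V) − M(N)],

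that is, the effect of adding ipilimumab minus the effect of the vaccine. Section 1.4.2 says the vaccine combination was expected to augment the T-cell response, so the second bracket cannot be assumed to be zero for this outcome.

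**Model.** With week as the only fixed effect, the stated regression has no coefficient for cohort, regimen or trial. No other model is given for the cross-trial test.

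**Same-plate control.** Suppose a plate or run adds an offset a to every reading. Within a subject, (post + a) − (pre + a) = post − pre, so a cancels in change from baseline. A proportional offset cancels in the same way on the log scale, one of the four transformations allowed. Differences between trials in population, centre or period do not cancel, and 6.3.4 does not say that the cross-trial test uses change from baseline.

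**The plan's own figures.** Section 6.3.4 gives chance probabilities for 11 independent tests at 0.05. The binomial tail P(X ≥ r), X ~ Bin(11, 0.05), is 0.431, 0.102 and 0.0152 for r = 1, 2 and 3. This reproduces the stated 0.43, 0.10 and 0.015. No sample size, SD or power is given for the cross-trial hypothesis, so there is nothing of its own to reproduce.

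**Illustration of an uncorrected between-trial shift.** Assumptions, none of them from the documents: comparator size n2, a two-sample t-test, no regimen effect, and a between-trial shift of d SD on the scale compared. From the plan: 20 current subjects and two-sided 0.05.

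Noncentrality = d / √(1/20 + 1/n2), with 20 + n2 − 2 degrees of freedom. For n2 = 20 and d = 0.5: 0.5 / √0.1 = 1.58, critical value 2.02, rejection probability 0.338.

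| Shift d | n2 = 10 | n2 = 20 | n2 = 60 |
|---|---|---|---|
| 0.25 SD | 0.10 | 0.12 | 0.16 |
| 0.5 SD | 0.24 | 0.34 | 0.48 |
| 1.0 SD | 0.70 | 0.87 | 0.97 |

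**The case against.** The strongest reply is that this is a drafting slip in an exploratory analysis. The 11-marker rule already has the direction that fits a nivolumab comparator, so swapping the two drug names would settle it. The primary objective is safety, and the secondary immune objective, response at Week 12, does not need the cross-trial contrast. A historical comparison is legitimate if its cohorts are identified and a regimen term is added. All of that stands, and it limits the importance of the point. But swapping the names does not supply the missing comparator or the missing model, and exploratory status does not excuse a mislabelled effect.

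Several stronger readings are tempting but not supported:

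- *That no nivolumab-alone cohort of 15651 exists.* The documents do not say what every earlier cohort received. The cohort is not described; it is not shown to be absent.
- *That the contrast certainly includes removal of the vaccine.* The vaccine experience is never tied to 15651 by name, so this is conditional.
- *That this is the only between-regimen comparison.* The 11-marker rule implies one too, without naming a comparator. The T-cell hypothesis is the one that names an external comparator.
- *That the plan fits a model unable to estimate the contrast.* The subject-and-week model is given for trends under this regimen. The cross-trial test has no assigned model.
- *That the plan claims same-plate assay removes differences between trials.* It claims this only for pre and post samples of one subject, and there it helps.
- *That 0.12, 0.34 and 0.87 are this trial's false-positive rates.* They would apply to any 20 v 20 historical comparison with those shifts, and a purely additive assay offset would not produce them in change from baseline.

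**Conclusion.** The point holds. As written, 6.3.4 names the effect of adding nivolumab while its comparator could show only the effect of adding ipilimumab, and it contradicts its own marker rule. The comparator is not described, the cross-trial model is not stated, and population, centre and period differences remain in the contrast. These conclusions come from the text and need no assumed figure.

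The size of any bias cannot be derived from the documents. Over an assumed comparator n of 10 to 60, chance findings from shifts of 0.25 to 1.0 SD range from 0.10 to 0.97, which shows only that the p-value would be sensitive to differences between trials. The point concerns one exploratory immune claim. It should be corrected, but it does not touch the primary safety objective or the within-subject immune analysis.

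**What to change.** In section 6.3.4:

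1. State that the immune objective is answered by within-subject change from baseline under the combination.
2. Reword the cross-trial contrast as the effect of adding ipilimumab, consistent with the 11-marker rule.
3. Name each comparator cohort, with its actual regimen (including any vaccine) and its n.
4. Present the comparison as change from baseline by cohort, with estimates and confidence intervals. Label it exploratory, non-randomised and confounded by trial, and do not report it as a hypothesis test at 0.05.

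The cost is about a paragraph of wording and the details of the comparator cohorts. The downside is giving up one exploratory significance claim.

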6.3.4.1. T-cell Proliferation

The definition of augmented proliferation for the purposes of this trial will be a 20% increase, at Week 12, in the absolute proportion of CD107a positive CD8+ T cells that stain with the Ki-67 marker.

6.4. Missing Data Handling

Unresolved missing data may be imputed when the analysis integrity is affected. The conservative principle will be used for data imputation. For example, if an adverse event onset day is missing but the adverse event onset year and month cannot exclude this adverse event as a TEAE, the adverse event will be flagged as a TEAE.

